#### 5.2.6.2 Relative days

**Relative days** will be calculated from the reference date and will be used to classify the assessments.

The reference date also called Day 1, is defined as the first day of study treatment.

The relative days are derived using the formula below:

- (date of assessment) - (reference date) + 1 if the date of assessment is  $\geq$  reference date
- (date of assessment) - (reference date) if the date of assessment is  $<$  reference date

Relative days will be missing for the records of subjects not treated.

#### 5.2.6.3 Treatment periods

The following timing variables will be included in analysis datasets for modelling the trial.

Phase (APHASE)	Analysis period	Numeric analysis period (ASPER)	Planned treatment for period (APERIOD)
SCREENING			
TREATMENT	DOUBLE-BLIND TREATMENT	1	TRT01P
FOLLOW-UP			

The treatment period will be defined by a start date (ADSL.TRTSDT) and an end date (ADSL.TRTEDT).

#### 5.2.7 Analysis Windows

For subjects who received at least one patch, all records (including unscheduled, re-tests and early termination visits) are classified in time windows, according to their relative days.

The analysis visit labels (AVISIT) to be used in the analysis datasets and in the TFLs are described below.

	Statistical Analysis Plan	
	EPITOPÉ (V712-304) – Statistical Analysis Plan	
	Référence du Document / Document Reference : CCI	Page : 25 / 74

CCI

**Table 2 - Time Window for Efficacy / Safety / Laboratory analyses**

Analysis Visit (AVISIT)	Target	Time Window 
Baseline	Day1 pre-dose	Not applicable
Day 8	Day 8	±5 d
Month 1	Day 30	±14 d
Month 3	Day 90	±21 d
Month 6	Day 180	±21 d
Month 9	Day 270	±21 d
Month 12 (V10)	Day 365	- 21 d to + 90 d
Month 12 (V11)	Day 372	V10 + 1 to the earliest between V11 and V10 + 2 w
Month 12 (EOS)	Day 400	End of the V11 time window + 1 to V11 + 8 w

(1) In the event that a record does not fall within any predefined analysis timepoint window, AVISIT is populated as "Not Windowed". Assessments not assigned to any visit will be kept in the analysis dataset and in Listings.

**For primary and secondary analyses, the DBPCFC entered in the eCRF at Visit 10 or Visit 11 (Month 12) will be taken into account without using the analysis window.**

For other efficacy analysis, if an assessment cannot be performed during a planned visit (e.g. SPT postponed due to wash-out period), unscheduled visits occurring within 7 days will be taken into account. Re-tests and other unscheduled visits will not be considered in the analysis (only described in listings). For safety analysis and exposure to treatment, data including re-tests and unscheduled visits will be used in the analysis.

- If more than one assessment is included in a time window the assessment closest to the target day should be used.
- If there are more than one observation with equal distance to the target day the more recent will be used in the analyses.
  - For efficacy related analyses, if multiple measurements for a particular parameter are collected on the same day for the same subject, the more recent of those measurements will be used.
  - For safety related analyses, if multiple measurements are made for a particular laboratory or vital sign parameter on the same day for the same subject, the more recent of those measurements will be used in the analyses.
- If there are visits reported twice in the eCRF, i.e. in an analysis visit and in an unscheduled visit (in case assessment pages are available in one of the visit and not others), all assessments recorded in both visits will be used in the analyses.

The record chosen in a time window is indicated by the analysis flag variable (ANLzzFL).

CONFIDENTIEL / Ne pas diffuser sans autorisation de DBV

CONFIDENTIAL / Do not distribute without DBV authorization

	Statistical Analysis Plan	
	EPITOPÉ (V712-304) – Statistical Analysis Plan	
	Référence du Document /Document Reference : CCI	Page : 26 / 74

CCI

For summaries and listings of shift from baseline and potentially clinically significant values, all values will be considered in the analyses.

All data collected at unscheduled visits will be listed.

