#### 8.2.2.3 *Unscheduled Assessments*

Extra assessments (laboratory data or vital signs associated with non-protocol clinical visits or obtained in the course of investigating or managing AEs) will be included in listings, but not summaries. If more than 1 laboratory value is available for a given visit, the first valid observation will be used in summaries and all observations will be presented in listings. It is noted that invalid laboratory data may not be used (from hemolyzed samples, mishandled samples, quantity not sufficient, or other conditions that would render the values invalid).

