#### **5.5.4 Clinical Laboratory Evaluation**

Laboratory tests will be performed by a central laboratory. All laboratory data units will be converted to SI units if necessary.

The following laboratory parameters will be assessed at the analysis windows Baseline, Month 3, Month 6 and Month 12:

CONFIDENTIEL / Ne pas diffuser sans autorisation de DBV

CONFIDENTIAL / Do not distribute without DBV authorization

	Statistical Analysis Plan	
	EPITOPE (V712-304) – Statistical Analysis Plan	
	Référence du Document /Document Reference : CCI	Page : 56 / 74

CCI

- Hematology:
  - hemoglobin,
  - hematocrit,
  - platelets,
  - red blood cells,
  - white blood cells (with differential cell count (in %))
- Biochemistry:
  - alanine aminotransferase (ALT),
  - aspartate aminotransferase (AST),
  - total bilirubin,
  - total protein,
  - blood urea nitrogen,
  - creatinine

Clinically significant changes (abnormalities) in laboratory parameters, in the judgment of the Investigator, will be recorded as AEs and appropriate countermeasures taken.

In the event of unexplained abnormal laboratory test values of clinical significance, the tests should be repeated at a reasonable time point and followed up until they have returned to the normal range and/or an adequate explanation of the abnormality is found.

Those repeated assessments performed outside scheduled visits are taken into account for the analysis and should follow the rules described in section 5.2.7.

The following results will be tabulated for hematology and biochemistry tests on the safety set (in SI units):

- Descriptive statistics for each test result at each timepoint.
- Descriptive statistics for absolute changes from Baseline for each test result at time point.
- Common Toxicity Criteria for Adverse Events (CTCAE version 4.03) grade at each time point and shift from Baseline for each test result at each time point. CTCAE grades for hematology and biochemistry measures will be derived according to Appendix 8.3.
- Shift of test abnormalities (Low, Within normal range, High) between Baseline and each timepoint

All laboratory data will be listed. Values that are out of normal range will be flagged in the data listings.

Flags used are:

- Low (below normal ranges), based on the following original flags from the laboratory reports:
  - PL, L2 ("Panic Low")

CONFIDENTIEL / Ne pas diffuser sans autorisation de DBV

CONFIDENTIAL / Do not distribute without DBV authorization

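### The SAP lets re-tests and unscheduled values replace the scheduled value in by-visit laboratory and vital-sign tables, contrary to protocol 8.2.2.3 and without declaring the change

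*SAP*

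**What the plan says.** Protocol 8.2.2.3 covers laboratory and vital-sign data from non-protocol visits or from working up adverse events. Such data "will be included in listings, but not summaries". For laboratory data it adds: "If more than 1 laboratory value is available for a given visit, the first valid observation will be used in summaries".

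SAP 5.2.7 classifies all records, unscheduled visits and re-tests included, into windows by study day, and states: "For safety analysis and exposure to treatment, data including re-tests and unscheduled visits will be used in the analysis". The record is then chosen as follows: "If more than one assessment is included in a time window the assessment closest to the target day should be used". On ties: "If there are more than one observation with equal distance to the target day the more recent will be used in the analyses". For laboratory and vital-sign parameters measured more than once on a day, the more recent measurement is again used.

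SAP 5.5.4 applies these rules to repeat laboratory tests: "Those repeated assessments performed outside scheduled visits are taken into account for the analysis". It also says why repeats arise. Unexplained, clinically significant abnormal tests are repeated and "followed up until they have returned to the normal range", or until an adequate explanation is found, or both.

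SAP 5.2.7 makes one exception: "For summaries and listings of shift from baseline and potentially clinically significant values, all values will be considered in the analyses". It also lists all unscheduled data.

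SAP 5.11 lists six changes from the protocol. The record-selection rule is not among them.

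**The concern.** The two documents give different answers to a basic question: when a child has two laboratory values around Month 3, which one is the Month 3 value? Under the protocol it is the first valid one, and extra assessments are only listed. Under the SAP it may be the re-test.

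The difference is not neutral, because a normal value prompts no repeat and an abnormal one does. A rule that can prefer the later record will, when it acts, tend to replace an abnormal value with one closer to resolution. Vital signs are open to the same mechanism: protocol 6.2.3 allows repeats for safety reasons and during the food challenge.

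What is at stake is whether the by-visit means and changes from baseline describe what the scheduled visit found. They can look more normal than that. A rule that departs from the protocol in this direction should be either removed or declared.

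**Working it through.** The documents state no figure on this point, so there is none to reproduce. The check sets the rules side by side and then works out when the SAP rule changes the reported value.

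**Rules compared**

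| Situation | Protocol 8.2.2.3 | SAP 5.2.7 and 5.5.4 |
|---|---|---|
| Extra laboratory or vital-sign assessment | Listed only | Enters safety analyses |
| Several laboratory values at one visit or in one window | First valid | Closest to target day |
| Tie in distance | No separate rule | More recent |
| Same-day laboratory repeat | First valid | More recent |
| Same-day vital-sign repeat | No first-value rule; extra assessments not summarised | More recent |

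**Inputs**
- Target for Month 3: Day 90, analysis window ±21 days (SAP Table 2).
- Scheduled Visit 7: Month 3 ±7 days (protocol Schedule of Procedures and 7.2.8). I take this as Day 83 to Day 97, that is, centred on the SAP target.
- Assumption: the 15 possible visit days are equally likely. The documents give no distribution.

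**Condition for replacement.** Let the scheduled draw be d days before the target, and the re-test r days after the draw (r ≥ 1). Their distances from the target are d and |r − d|. The re-test is chosen when |r − d| ≤ d, because a tie goes to the later record. This gives r ≤ 2d. With d at most 7, the furthest reach is r = 14. If the draw falls on or after the target, a later-day re-test is further away and never wins.

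**Example.** An abnormal value on Day 84 and a normal re-test on Day 92 lie 6 and 2 days from Day 90. Here d = 6 and r = 8, and 8 ≤ 12, so Day 92 is reported as Month 3.

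**Share of visit days on which the re-test wins.** Count the values of d from 1 to 7 with d ≥ r/2, and divide by 15.

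| Re-test after the draw | Qualifying d | Share |
|---|---|---|
| Same day | all visit days (same-day rule) | 15/15 |
| 1 day | 1 to 7 | 7/15 = 47% |
| 3 days | 2 to 7 | 6/15 = 40% |
| 7 days | 4 to 7 | 4/15 = 27% |
| 14 days | 7 only | 1/15 = 7% |
| 15 days or more | none | 0/15 |

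Under the protocol rule the share is zero throughout, because a valid first value is never displaced in summaries.

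**Outputs affected.** SAP 5.5.4 plans descriptive statistics and absolute changes from baseline at each time point. SAP 5.5.5 plans the same kind of summary for vital signs. These need one record per child and time point, and the all-values exception does not name them.

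The CTCAE output is unclear. SAP 5.5.4 puts grade at each time point and shift from baseline in one item. The exception applies all values to shifts but does not say how several values are counted in a per-time-point table, or whether the grade column follows the same rule.

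**The case against.** The strongest reply is that no abnormal value disappears. The shift and potentially clinically significant summaries use all values, all laboratory data are listed with out-of-range flags, and unscheduled data are listed. The planned re-test applies to clinically significant abnormalities, and clinically significant changes are recorded as adverse events (protocol 6.2.2, SAP 5.5.4). This stands. A reader might infer that re-tests erase abnormal findings from the safety report; the documents do not support that.

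Three further replies also stand in part:
- Re-testing can end with an explanation while the value is still abnormal, so the pull towards normal values is a tendency, not a certainty.
- The 47% is a ceiling, reached only for a re-test the next day. SAP 5.2.9 says some visits were delayed, which moves draws past the target, where a later-day re-test cannot win. Laboratory testing is central, so a re-test prompted by a result would ordinarily fall on a later day (turnaround is not stated). The same-day rule therefore bears mainly on vital signs. Even there, SAP 5.5.5 describes recording before each challenge, and it is not stated that repeats during a challenge enter the same dataset.
- The protocol leaves detailed methods to the SAP, and for detecting abnormalities the SAP is more inclusive than the protocol. Protocol 8.2.2.3 has no exception that would admit extra values to shift tables.

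None of this explains why by-visit descriptive tables should use the re-test, or why SAP 5.11 is silent. In SAP 5.2.7 itself, re-tests are kept out of the other efficacy analyses and only listed; no reason is given for the opposite choice in safety.

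**Conclusion.** The conflict between protocol 8.2.2.3 and SAP 5.2.7 and 5.5.4 is real and undeclared. Its effect is limited to by-visit descriptive statistics and changes from baseline for laboratory and vital-sign data, which can look more normal than the scheduled visit was. The reach of the rule is known: within 2d days for a draw d days early, never for a later-day re-test of a draw on or after target, always for a same-day repeat. The shares of visit days rest on evenly spread visits centred on the SAP target. The size of the effect on the tables is unknown, because the documents do not give the number of re-tests, and it may be small.

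A reader might also infer that the CTCAE grade table will contradict the shift table for the same child. That is one possible reading of SAP 5.5.4; the text is ambiguous and should be settled. No primary, secondary or adverse event analysis is shown to change.

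**What to change.** In SAP 5.2.7 and 5.5.4, and for vital signs in 5.5.5:

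1. For by-visit descriptive and change-from-baseline tables, use the first valid laboratory value from the scheduled visit, and the scheduled, pre-challenge vital-sign value. Use an unscheduled value only when the scheduled one is missing.
2. Keep all values for the shift and potentially clinically significant summaries and for listings, as now.
3. State that CTCAE grade and CTCAE shift at each time point use the same record rule, for example the worst value in the window.
4. List in SAP 5.11 whatever still departs from protocol 8.2.2.3. With steps 1 and 2 that includes the use of extra values in shift and potentially clinically significant summaries and as a fallback for a missing scheduled value. The vital-sign rule in step 1 is an addition, because the protocol's first-valid rule covers laboratory values only.

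The cost is SAP wording, one record-selection flag and a stated counting rule for the CTCAE tables. No new data and no new worst-on-treatment table are needed.

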### 5.2.8 Baseline definition

The baseline assessment will be the latest, non-missing pre-dose assessment available.

All data collected before (<) Day 1 are considered as pre-dose.

At day 1, all following examples are considered as pre-dose:

- if the time is collected and is before (<) treatment start time
- if the time is not collected but the examination/assessment/event is planned before treatment in the protocol (Physical examination, Vital signs, Laboratory tests, Questionnaires planned at day 1 before the first IP, SCORAD, SPT)
- other findings will be considered as post-dose and not included in the baseline calculation.

If a patient is not treated, the baseline value for a parameter is the last non-missing value.

### 5.2.9 Potential impact of Covid-19 pandemic

Covid-19 pandemic have impacted the timing of the study and efficacy measurements.

Assessments visits were delayed for some subjects enrolled in this study. Therefore, analysis windows were extended as defined in section 5.2.7.

Sensitivity efficacy analyses will be performed to account for the subjects impacted by Covid-19 pandemic in section 5.4.1.

## 5.3 Subject characteristics

### 5.3.1 Subject disposition

A clear accounting of the disposition of all subjects who enter the study will be provided, from screening to study completion. Subject disposition will be summarized for all subjects, overall and by treatment group. Percentages will be based on the number of subjects in the Full Analysis Set (FAS). The following descriptions will be performed on all enrolled subjects:

- Number of enrolled subjects, number of screen failures, reasons for non-randomization,
- Analysis sets: number and percentage of subjects in each population used for the analyses. The populations are defined in Section 4.
- Number and percentage of subjects who completed the study treatment, subjects who discontinued the study treatment and reasons why subjects discontinued the study treatment,
- Number and percentages of subjects who discontinued the study treatment:
  - Before Month 12 (exposure < 358 days)

CONFIDENTIEL / Ne pas diffuser sans autorisation de DBV

CONFIDENTIAL / Do not distribute without DBV authorization

	Statistical Analysis Plan	
	EPITOPÉ (V712-304) – Statistical Analysis Plan	
	Référence du Document /Document Reference : CCI	Page : 27 / 74

CCI

- At Month 12 or after (exposure  $\geq$  358 days)
- Number and percentages of subjects who performed the Month 12 Food Challenge:
  - As per Month 12 time-window
  - Out of Month 12 time-window (visit delayed due to covid-19 pandemic)
- Number and percentage of subjects randomized by region, country and site,
- An enrolment summary will be presented overall, by region, country and site, showing the number of subjects enrolled, randomized and completing the study, the first date of consent, the last study visit date, the study duration (in days, calculated as the end of study date for randomized subjects – first date of consent for the first screened subject +1).

Study disposition and termination details will be listed for each subject. Listings will also be created to show the study analysis set classifications and randomization assignments.

### 5.3.2 Protocol Deviations

Protocol Deviations (PD) including violations of inclusion/exclusion criteria will be assessed as “minor” or “major” in cooperation with the Sponsor prior to database lock and unblinding.

Major PDs are defined as those deviations from the protocol likely to have an impact on the perceived efficacy and or safety of the study. Major protocol deviations that may affect the primary analysis will lead to exclusion of the subject from the PP set.

Appendix 8.1 provides preliminary categorization of major protocol deviations and actions to be taken with regards to analysis. Major deviations will be listed separately from minor deviations.

The number and percentage of subjects with major protocol deviations will be summarized by type of deviation, overall and by treatment group for the randomized population. All protocol deviations will also be listed.

The COVID-19 pandemic requires specific attention on the Protocol Deviations that may impact the conduct of the study and the follow-up of the subjects. The number and percentage of subjects that experienced at least one Covid-19 deviation will be described together with the major protocol deviation table. Also, Protocol Deviations that are specifically related to COVID-19 will also be described in a separate table and identified in the listing of deviations.

### 5.3.3 Demographic variables and Baseline Characteristics

#### 5.3.3.1 Demographics

Descriptive statistics will be produced for demographic baseline characteristics by treatment group and overall. Demographics data include:

- Age (years), continuous, recalculated based on date of birth and informed consent, populated by IWRS system
- Age in category (1-year, 2-years,3-years)
- Gender (Male, Female, Undifferentiated, Unknown)

CONFIDENTIEL / Ne pas diffuser sans autorisation de DBV

CONFIDENTIAL / Do not distribute without DBV authorization

	Statistical Analysis Plan	
	EPITOPE (V712-304) – Statistical Analysis Plan	
	Référence du Document /Document Reference : CCI	Page : 28 / 74

CCI

- Race as collected in the eCRF:
  - American Indian or Alaska Native
  - Asian,
  - Black or African American,
  - Native Hawaiian or Other Pacific Islander,
  - White,
  - Other,
  - Not collected (“Not applicable”, “Not reported” or missing)
- Race using the following mapping: White (e-CRF value = “White”), Black or African American (e-CRF value = “Black or African American”), Asian (e-CRF value = “Asian”), Other (e-CRF value = “Native Hawaiian or Other Pacific Islander”, “American Indian or Alaska Native” or “Other”), Not collected (“Not applicable”, “Not reported” or missing)

Summaries will be provided for the FAS. Replicating this table for various analysis sets is not useful, however, if the PP Set is more than 10% less than FAS, a new table with PP Set will be presented.

The demographics data will be provided in data listing.

#### 5.3.3.2 Baseline Characteristics

Descriptive statistics will be produced for baseline characteristics by treatment group and overall. Baseline characteristics data include:

- Height (cm), Weight (kg)
- Peanut-specific IgE (kU/L)
- Peanut-specific IgG4 (mg/L)
- Skin Prick Test (SPT): Mean and longest wheal diameter for undiluted peanut extract (mm)
- ED in continuous
- ED in categories:
  - 1, 3, 10, 30, 100, 300 mg;
  - < 10mg, ≥ 10mg
- CRD in continuous

Summaries will be provided for the FAS. The full baseline characteristics data will be presented in a listing.

#### 5.3.4 Medical history

Medical history covers the collections of information on past or current conditions (with the exclusion of peanut allergy). In addition to the coding performed, the following medical history classes are defined:

- Any allergy other than peanut
  - PT terms which contains “ALLERG” (excluding LLT “Peanut allergy”) and PT terms which contains “HYPERSENSITIVITY” (excluding LLT “Peanut allergy”)
- Any food allergy other than peanut:

CONFIDENTIEL / Ne pas diffuser sans autorisation de DBV

CONFIDENTIAL / Do not distribute without DBV authorization

	Statistical Analysis Plan	
	EPITOPE (V712-304) – Statistical Analysis Plan	
	Référence du Document /Document Reference : CCI	Page : 29 / 74

CCI

- PT “Food allergy” (excluding LLT “peanut allergy”)
  - + PT “Milk allergy”
  - + PT “Allergy to fermented products”.
- Other atopic conditions:
  - Asthma
    - SMQ Asthma/bronchospasm MedDRA Version 20.1 from narrow terms: List of PT terms: Asthma, asthma exercise induced, asthma late onset, asthmatic crisis, bronchospasm, bronchial hyperreactivity, infantile asthma, status asthmaticus, wheezing
  - Eczema/Atopic Dermatitis
    - List of PT terms: Dermatitis atopic, Dermatitis allergic, Eczema, Application site eczema.
  - Allergic Rhinitis
    - List of PT terms: Rhinitis allergic, Seasonal allergy, Rhinitis perennial, Conjunctivitis allergic

The exhaustiveness of the lists specified above will be reviewed during the data review meeting and may be extended with further terms prior to database lock as applicable.

The medical history of specific interest description will also be presented for:

- medical history ongoing at Baseline
- medical history not ongoing at Baseline

Medical history will be coded using the latest version of the Medical Dictionary for Regulatory Activities (MedDRA) and will be reported by SOC and PT. The table will be sorted by descending frequency of SOC, and, within each SOC, by descending frequency of PT in all subjects. The number and percentage of subjects with at least one medical history term will also be provided.

Medical history will be summarized overall and by treatment group for the Safety set. Medical history data will be also provided in listings.

